The following analyses will be carried out for each of the ITT and PP (primary) populations. There will be no imputation for missing data or adjustments for multiple comparisons.

Additional Endpoints to be studied are:

- The change in mean symptom scores on the HAM-D₁₇ through 6 weeks of treatment
- The change in mean symptom scores on the MADRS through 6 weeks of treatment.
- Clinical response, defined by 50% or greater reduction on the MADRS total symptom scores through 6 weeks of treatment.
- Effectiveness of Blinding questionnaire

Descriptive statistics (sample size, mean, median, quartiles, standard deviation, minimum, maximum) of the mean change in HAM-D₁₇ and MADRS from baseline to Week 6 will be presented. Change from baseline in the HAM-D₁₇ and MADRS total scores will be compared across treatment groups using a MMRM model with terms for treatment, investigative center, visit, and the treatment by visit interaction (visits in the open-label phase will be excluded for the primary double-blind analysis). The model will also include baseline HAM-D₁₇ (or MADRS) score as a covariate and subject will be a random effect. An unstructured covariance matrix will be used for the within-subject correlation. Kenward-Rogers'

approximation will be used to estimate degrees of freedom. The LSMEANS statement for the treatment-by-visit interaction will be employed to examine differences across treatments at specific time points, with the focus being on the Week 6 change from baseline. Parameter estimates will be presented and two-sided 95% confidence intervals will be constructed using model estimates for the mean and residual error. Tests of hypotheses will be two-sided and will be based on the contrasts between active sTMS and sham within the model.

For MADRS response rate through 6 weeks of treatment, the number and percentage of responders will be calculated and will be compared in a similar manner as the primary endpoint. Tests of hypotheses will be two-sided and will be based on the contrasts between active sTMS and sham within the model.

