The Per-Protocol (PP) study sample is comprised of randomized subjects who receive the correct randomized treatments according to the protocol schedules without any major protocol violation. This is the primary analysis population per e-mail discussion between NeoSync and the Food and Drug Administration (FDA) on July 17, 2015. Major protocol violations include but are not limited to:

- Receiving treatments other than the randomized treatments.
- Treatments not administered according to study protocol.
- Subjects cannot miss more than 1 dose in a treatment week and their weekly visit interval cannot exceed 10 calendar days. Any subject who misses more than 6 doses in the 6 week treatment period is not considered compliant with the treatment and will not be included in the PP analysis population.
- Receiving concomitant medications that are not allowed per the study protocol; the prohibited medications are as follows:

Use of the following concomitant medications is prohibited within 72 hours of the baseline EEG (Day 0), but is otherwise allowable in the study:

- Anti-Migraine

- Benzodiazepines and Partial Benzodiazepine Agonists
- Non-Benzodiazepine Hypnotics
- Non-Sedating Antihistamines
- Cough Suppressants (Dextromethorphan, etc.)

Uses of the following concomitant medications are excluded throughout the study and should be washed out at least 1 week prior to baseline (Day 0):

- Anticholinergics
- Anticonvulsants
- Antidepressants (note: fluoxetine shall be washed out 4 weeks prior to baseline)
- Antihistamines (with sedating effects)
- Anti-Parkinsonian medications
- Antipsychotics
- Barbiturates
- Codeine or Oxycodone containing compounds
- Corticosteroids (tablet forms only)
- Cold Pills (with sedating ingredients)
- Medications that are known to reduce seizure thresholds:
 - a. Accurbron/Accubron
 - b. Doxepin
 - c. Ambenonium Chloride
 - d. Amitriptyline
 - e. Imipramine
 - f. Amoxapine
 - g. Trazodone
 - h. Amphetamine sulfate
 - i. Baclofen
 - j. Chlorpromazine
 - k. Clozaril
 - l. Cocaine
 - m. Lithium
 - n. Protostat
- Mood stabilizers
- Muscle relaxants
- Other sleep aid medications with anticholinergic properties (prescription OR over-the-counter)
- Opioid analgesics
- Pseudoephedrine combination forms that contain excluded medication (pseudoephedrine (e.g., Sudafed) in pure form is acceptable during the study)
- Psychostimulants

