For the six-week double-blind phase, imputation of data on the primary endpoint will be performed as described below. For the six-week follow-up open-label phase (Weeks 6 – 12), all efficacy and safety summaries will be based on the all sTMS treated subject population, which consists of all subjects who have entered the six-week follow-up Phase. All efficacy analyses will be performed on the Observed Cases (OC) dataset only for each week in this open-label Phase. That is, no imputation will be used, and only data observed during the follow-up Phase will be summarized. Analyses in the open-label phase will be presented by double-blind

treatment group and for both treatment groups combined. Baseline for the double-blind phase will be defined as the last available value measured post-washout and prior to the first double-blind dosing. Baseline for the open-label phase will be defined as (a) the last post-washout assessment measured prior to the beginning of the double-blind treatment phase for patients randomized to sTMS in the double-blind phase; and (b) the last double-blind assessment measured prior to the beginning of the open-label phase for patients randomized to Sham in the double-blind phase.

Analysis of Primary Efficacy Endpoint

HAM-D/MDRS will be assessed at screening, baseline, Week 1-6 Evaluation Visits, and during the open-label phase through Week 12 evaluation visit. The primary efficacy endpoint is clinical response, defined by 50% or greater reduction on the HAM-D¹⁷ from baseline to Week 6. The efficacy analyses will be performed on the PP, ITT with available data, and ITT with imputed data (see below for imputation methods) analysis populations. The PP analysis population is the primary analysis population for efficacy per e-mail discussion between NeoSync and the FDA on July 17, 2015.

The null hypothesis is that the active sTMS treatment group does not differ from the sham group with respect to the proportion of patients with clinical response at Week 6. The corresponding alternative hypothesis is that the active sTMS treatment group differs from the sham group with respect to the proportion of patients with clinical response at Week 6.

Specifically, the primary efficacy analysis will be a test of the hypotheses:

$$H_0: \pi_A - \pi_S = 0$$

and

$$H_a: \pi_A - \pi_S \neq 0$$

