In addition, a tipping point analysis will be performed to assess the likelihood that the observed significance would no longer hold based on various assumed values of the missing clinical response data. Specifically, to start, at Week 6, all missing data will be assumed to be successes for both the sTMS and sham groups. Fisher's exact test will then be run comparing treatments on this imputed clinical response rate and the treatment comparison Week 6 p-value will be generated. Then, the analyses will be repeated where 1 missing sTMS patient is assumed to be a failure, and all remaining sTMS and all Sham patients are assumed to be successes. Then the analyses will be repeated where 2 missing sTMS patients are assumed to be a failure, and all remaining sTMS and all Sham patients are assumed to be successes. This process will continue until the "tipping point" is reached. The "tipping point" is the imputation point at which the Fisher's Exact test p-value changes from significance to non-significance.

The above process will then be repeated but where 1 missing Sham patient is assumed to be a failure throughout the above one-failure-at-a-time imputation for sTMS patients. It will then be repeated but where 2 missing Sham patients are assumed to be a failure throughout the imputations for sTMS patients, etc.

G. Subgroup Analyses

The robustness of the primary efficacy outcome will be confirmed via subgroup analyses. Subgroups of subjects will be identified according to their investigative center, gender, age (<median, ≥median), education, concomitant medication, ATHQ history and duration of illness (<median, ≥median). The Fisher's Exact test on the primary endpoint analysis will be repeated within the subgroups of subjects defined by levels of the variable (e.g. adults < median age, adults ≥ median age). The purpose of this subgroup analysis is not to find significant treatment effect within subgroups, but rather to assess consistency of treatment effect across subgroups. This will be performed on the ITT population with available data and imputed data, and on the PP analysis population.

H. Secondary Analyses for Label Considerations

The following analyses will be conducted for the ITT (available and imputed data) and PP populations.

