The following secondary measures are to be considered for labeling. They will be analyzed using the gatekeeper (sequential) strategy to control for multiple comparisons by pre-specifying the order of testing (Westfall and Krishen, 2001). If the primary analysis is significant, these outcomes will be tested in the order listed below, each at the 0.05 alpha level. Testing for label consideration will cease when the first outcome results in a two-sided p-value greater than 0.05.

- Change from Baseline on the HAM-D¹⁷ score at Week 6;
- Change from Baseline on the MADRS score at Week 6;
- Clinical response, defined by 50% or greater reduction on the MADRS total symptom score at Week 6.

Treatments will be compared on the mean change from baseline HAM-D¹⁷ and MADRS scores at Week 6 using analysis of covariance adjusting for the baseline value of the given endpoint. Treatment group comparisons on the proportion of subjects who achieve MADRS clinical response at Week 6 will be carried out using Fisher's Exact test. Tests of hypotheses will be two-sided.

Assessment of investigator center-by-treatment interaction will be carried out using Breslow-Day test for the MADRS clinical response at Week 6 and using analysis of covariance with the independent variables of treatment group, investigative center, and the treatment-by-investigative interaction for change from baseline in HAM-D¹⁷ and MADRS at Week 6. Again, a non-significant interaction (using a 0.15 level of significance) or a significant interaction deemed only quantitative in nature supports the pooling of results across centers for the analyses on these secondary endpoints.

Multiple imputation for the ITT population for each endpoint will be carried out using linear regression in a similar manner as for the primary endpoint. For MADRS clinical response, the overall significance of the difference between treatment groups across the imputed datasets will be carried out in the same manner as for the primary efficacy endpoint. For the mean change from baseline at Week 6 for each of HAM-D¹⁷ and MADRS, analysis of covariance comparing treatments adjusting for the baseline value of the endpoint will be carried on each imputed dataset with the results being combined across imputed datasets using PROC MIANALYZE to obtain one overall assessment of treatment difference on the mean endpoint, adjusting for baseline.

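### Protocol and SAP set different tests and different multiplicity rules for the secondary change scores, with no stated precedence, and the SAP test leaves out the site stratum

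*SAP*

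**What the plan says.** **Protocol, section 11.5, Additional Endpoint Analyses.** Change in HAM-D17 and MADRS is compared "using a MMRM model with terms for treatment, investigative center, visit, and the treatment by visit interaction". Baseline score is a covariate, the covariance is unstructured, and the contrast of interest is at Week 6. The section also says: "There will be no imputation for missing data or adjustments for multiple comparisons". The analyses are run "for each of the ITT and PP (primary) populations".

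**SAP, section H (Secondary Analyses for Label Considerations).** The same two Week 6 changes are compared "using analysis of covariance adjusting for the baseline value of the given endpoint". They stand first and second, with MADRS response third, in a "gatekeeper (sequential) strategy to control for multiple comparisons by pre-specifying the order of testing". The sequence opens only if the primary analysis is significant, and label testing stops at the first two-sided p above 0.05. Centre appears only in a separate interaction model. On datasets: "The following analyses will be conducted for the ITT (available and imputed data) and PP populations". No MMRM appears anywhere in the SAP; the exploratory by-visit changes in section I also use baseline-adjusted ANCOVA.

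**Common ground.** The SAP says of the per-protocol (PP) set, "The PP analysis population is the primary analysis population for efficacy", and the protocol likewise marks PP as primary. Both documents stratify randomisation by site (protocol section 5.3; SAP, Randomization). For MADRS response they broadly agree: the protocol treats it like the primary endpoint, and the SAP names Fisher's exact test.

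**The concern.** A confirmatory secondary claim needs one named test and one error-control rule, both fixed before unblinding. Here the first label test, HAM-D17 change, has two pre-specified models. The three secondary endpoints also fall under two multiplicity rules. Under the SAP, a failed primary or an earlier failure ends label testing. Under the protocol, each endpoint is tested at 0.05 whatever happened before it. The SAP's statement of purpose says that it sets out in advance the analyses on which conclusions will rest, which points towards the SAP. But no passage states precedence, and the SAP does not present its rules as changes to section 11.5. Where the protocol does defer to the SAP, as it does for centre pooling, it says so; it does not do so here.

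Separately, the SAP comparison omits the factor used to stratify randomisation, although the protocol's model contains it.

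**Working it through.** **The plan's own figure.** Neither document gives a power or sample size for the secondary endpoints. The primary figure reproduces: for 34% vs 8% at 81% power, the continuity-corrected two-proportion formula gives 46 per group. Full enumeration of Fisher's exact test at 46 per group gives 83.6%. Enrolment is 92/(1 − 0.23) = 119.5, so 120. None of this is affected by the point.

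**1. Multiplicity.** Three independent tests at 0.05 would give 1 − 0.95³ = 14.3%. That is not credible here, because both scales come from one combined interview (protocol section 7.2). Instead, 200,000 null trials per cell were simulated with 46 per arm. The two changes were bivariate normal with an assumed correlation and were compared by t-test. MADRS response was MADRS change beyond the cut that gives the stated response rate, compared by Fisher's test. Chance of at least one p below 0.05 with no adjustment:

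| Response rate | r = 0.7 | r = 0.8 | r = 0.9 | r = 0.95 |
|---|---|---|---|---|
| 8% | 9.4% | 8.9% | 8.1% | 7.5% |
| 21% | 9.7% | 9.3% | 8.6% | 8.0% |
| 30% | 9.8% | 9.4% | 8.5% | 8.0% |

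A second simulation of 40,000 trials per cell, at r = 0.95 and 0.7, gave 7.5–9.3% at 8% response and 8.1–10.0% at 21–30%. Under the SAP sequence, with no effect on the primary either, the rate is about 0.4%, 1.1% and 1.4% at the three response rates. If the primary has a true effect, it is at most 5%.

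**2. The two change-score tests in PP.**

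- Differences, from protocol section 1.1: 7.39 − 4.59 = 2.80 (non-naive completers) and 8.58 − 4.25 = 4.33 (non-naive PP, the planning population).
- SD: √((7.33² + 4.74²)/2) = 6.17.
- Design: 120 randomised in site blocks of 10 at 10 or 16 sites, 28 lost at random to leave 92, sites with fewer than 10 PP subjects pooled, 4,000 replicates per cell.
- Assumed: baseline correlation 0.3, AR(1) visit correlation 0.8, effect growing linearly to Week 6, site share of variance 0, 5, 10 or 20%.
- The MMRM used REML with an unstructured covariance and approximate degrees of freedom, not Kenward-Roger.

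Percentage of trials with verdicts on opposite sides of 0.05 (the four values follow site shares 0/5/10/20%):

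| Comparison | 2.8 points, 10 sites | 2.8 points, 16 sites | 4.33 points |
|---|---|---|---|
| SAP ANCOVA vs protocol MMRM | 4.4/5.9/5.8/8.9 | 5.8/6.0/6.8/8.8 | 1.5–2.4 |
| ANCOVA without vs with site | 4.2/5.1/6.2/8.4 | 6.3/6.0/6.9/8.6 | 1.7–2.5 |
| ANCOVA vs MMRM, neither with site | 1.4/1.7/1.8/1.5 | 1.8/1.8/1.6/1.7 | 0.4–0.7 |
| ANCOVA vs MMRM, both with site | 3.1/2.9/3.3/2.9 | 4.6/4.0/3.8/4.0 | 0.9–1.3 |

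Both the site term and the choice of model contribute.

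**3. Cost of leaving site out.** If site explains a share ρ of variance and arms are balanced within site, the true size is about 2(1 − Φ(1.96/√(1 − ρ))), and a test with 80% power when adjusted has power Φ(2.80 − 1.96/√(1 − ρ)). For ρ = 5, 10 and 20% this gives sizes of 0.044, 0.039 and 0.028, and powers of 78.5, 76.9 and 72.9%. In the simulation, ANCOVA power at 2.8 points, without/with site, was:

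| Site share | 10 sites | 16 sites |
|---|---|---|
| 0% | 60.7/59.2 | 61.3/59.7 |
| 5% | 62.0/62.4 | 61.4/60.6 |
| 10% | 62.8/64.2 | 61.6/62.5 |
| 20% | 63.8/68.6 | 61.3/63.8 |

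Adding site therefore changes power by −1.6 to +4.8 points, and by −0.7 to +1.8 points at 4.33. Simulated size was 3.5–5.9% without site and 4.3–5.9% with it (Monte Carlo standard error √(0.05 × 0.95/4000) = 0.34 points), so nothing suggests that omitting site raises the error rate.

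**The case against.** The strongest reply is that the two multiplicity rules can coexist. The SAP's stopping rule covers label claims only, and the protocol makes no label claim for these endpoints. Nominal reporting under the protocol and a gate for labelling under the SAP are compatible. This stands to a degree: a reader might infer that the trial carries a 7.5–10% error rate on its label claims, but no document plans to base labelling on the unadjusted tests. What remains is that the protocol excludes adjustment outright and neither text says that its rule has been replaced.

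A second reply is that the SAP plainly governs. Its purpose statement supports that, but it is not a precedence clause. The SAP's title page is not in the text reviewed, so its date and version cannot be judged.

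Third, omitting site is legitimate. It is conservative, the primary Fisher's test is also unstratified, and adding site loses a little power when sites do not differ. All true. The gain depends on a site share that the documents do not give.

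Fourth, a reader might see a clash over datasets or imputation. The documents do not support that. PP is primary for efficacy in both, and Week 6 HAM-D17 is complete in PP by definition. The SAP keeps an ITT run on available data and adds multiple imputation beside it, which it calls supportive for the primary endpoint.

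**Conclusion.** The point holds as a mismatch between documents that should be resolved before unblinding. The gate test for HAM-D17 and MADRS change, and the multiplicity rule for the three label endpoints, are not uniquely fixed. The primary analysis is unaffected, and the SAP's rule is the stricter one.

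The size is modest. Unadjusted claims would carry about a 7.5–10% chance of at least one false positive, against at most 5% under the gate; this rests on assumed HAM-D/MADRS correlations of 0.7–0.95. The two change-score tests would disagree at 0.05 in about 1.5–2.4% of trials at the planning-population difference and in 4.4–8.9% at the smaller completers' difference. It would be tempting to put nearly all of that down to the site term, but with site in both models 2.9–4.6% disagreement remains at 2.8 points. Nor should the missing site term be read as inflating type I error: it costs precision, and only if sites differ. The site shares of 0–20% are assumptions.

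**What to change.** Before unblinding:

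1. State in the SAP that the section H sequence governs label claims, and record it as replacing the no-adjustment rule in protocol section 11.5. Align section 11.5 at the next protocol amendment.
2. Name one model in both documents as the gate test for the two change scores. The SAP's ANCOVA needs least rewriting, because the imputed-data text is already built on it; keep the MMRM as a sensitivity analysis.
3. Add pooled site to that model, including the imputed-data ANCOVA, using the pooling rule in the SAP's General Overview of Methods.

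A sentence saying that PP drives the sequence would be a helpful but optional clarification. The ITT imputation needs only a note that it is an added supportive run.

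Cost: a SAP revision and, later, a protocol amendment with IRB submission (protocol section 12.7). No new data, visits or subjects are needed. The downside is a power loss of up to about 2 points on the change scores if site explains no variance.

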08 JAN 2018

Date

PROTOCOL NND-3002

PROSPECTIVE CONFIRMATORY STUDY OF sTMS

STUDY SYNOPSIS

Study Objective	The primary objective of this study is to confirm the safety and effectiveness of synchronized TMS (sTMS) therapy in subjects with Major Depressive Disorder who have not responded adequately to at least one anti-depressant medication in the current episode.
Study Design	
Prospective, randomized, double-blinded, sham-controlled, parallel group adaptive design study to confirm the safety and efficacy of sTMS in subjects with major depressive disorder who have not responded to at least one anti-depressant medication in the current episode. This is a multicenter study in which approximately 120 subjects will be enrolled in the trial to obtain 92 evaluable subjects who fully complete the primary study phase of the trial. Randomized subjects will be treated 5 days per week for 6 weeks.
 
After signing informed consent, subjects who qualify for enrollment will discontinue use of their current antidepressant treatment (if applicable). Subjects must have discontinued the antidepressant medication a minimum of 1 week prior to their baseline measurements and initiation of treatment with the sTMS. Following wash-out of the antidepressant medication, an additional evaluation will be performed to determine whether the protocol eligibility criteria are still met before treatment. Qualified subjects will be randomized to either sTMS or sham treatment groups. Treatment will be initiated on Day 1 of the study. Subjects will visit the clinic for 5 daily treatment sessions per week for a total of 6 "treatment" weeks. A visit interval of 5-10 calendar days has been set for each "treatment" week. Treatment will be discontinued at the end of Treatment Week 6 (30 treatment sessions). Subjects will be clinically evaluated for safety and efficacy at the end of each of the six weekly treatment courses.
 
At the end of Treatment Week 6, subjects will have completed the primary study phase treatments and will be offered either open label sTMS therapy (if criteria are met) or alternate treatment as clinically indicated.

Study Population	Approximately 120 male and female subjects, age 22 to 65 years, who are suffering from Major Depressive Disorder, will be enrolled into the study.
Study Center(s)	Multicenter, up to 16 clinical sites

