Qualified subjects will be randomized to either active sTMS or sham treatment groups in a 1:1 ratio on an individual basis. Randomization will be stratified by site in blocks of 10 determined by a computer generated randomization table defined prior to the start of the trial. Each site will be given a set of 10 randomized PPMs. Treatment will be initiated on Day 1 of the study. Subjects will come to the clinic for 5 daily treatment sessions for a total of 6 “treatment” weeks. A visit interval of 5-10 calendar days has been set for each “treatment” week to accommodate visit scheduling flexibility. Treatment will be discontinued at the end of Week 6 (30 treatment sessions). Subjects will be clinically evaluated for safety and efficacy at the end of each of the six weekly treatment courses.

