ACTIVITY	SCREEN	BASELINE (DAY -0)	WK1 TX DAY 5	WK2 TX DAY 10	WK3 TX DAY 15	WK4 TX DAY 20	WK5 TX DAY 25	WK6/ EARLY TERM TX DAY 30	WK7 OPEN LABEL TX DAY 5	WK8 OPEN LABEL TX DAY 10	WK9 OPEN LABEL TX DAY 15	WK 10,11, OPEN LABEL TX DAY 20,25,30
Informed Consent	X											
Inclusion/Exclusion Criteria	X	X										
Mini Mental Status Exam (Version 2)	X											
MINI	X											
ATHQ	X											
Blinding Questionnaire			X					X				
Randomization		X										
NeoSync EEG	X	X										
Med/Psych History	X											
Vital Signs		X						X				
Labs ^a	X											
Pregnancy Test (HCG) ^b	X											
Urine Drug Screen ^b	X											
Weight		X						X				
Physical Exam ^a	X											
Demographics	X											
ECG ^a	X											
HAM-D/MADRS	X	X	X	X	X	X	X	X	X	X	X	X
IDS-SR		X	X	X	X	X	X	X	X	X	X	X
C-SSRS	X	X	X	X	X	X	X	X	X	X	X	X
Concomitant Med ^c	X	X	X	X	X	X	X	X	X	X	X	X
Adverse Events ^a	X	X	X	X	X	X	X	X	X	X	X	X

a Optional

b Must be performed at Screening and may be performed at any subsequent visit at the discretion of the Investigator

c In addition to the assessment visits outlined here, All subjects will have 5 treatment visits per week during treatment period changes in adverse events and concomitant medications should be recorded when made known to the site.

Note: The first treatment session may begin on the same day as baseline visit, after subject meets all criteria and is randomized to a treatment arm.

RANDOMIZATION

This study is randomized, double-blind, and sham-controlled to minimize bias. Subjects will be randomized following the post-washout screening/baseline analysis (Day 0) to one of the two treatment groups (sTMS vs. sham treatment), at a 1:1 ratio stratified by study center. The assignment is determined by a computer-generated randomization table defined prior to the start of the trial.

INITIAL SCREENING/BASELINE VISIT:

Potential study participants will be screened for eligibility per the protocol eligibility criteria. The Screening/Baseline visits may be split into two or more days. After informed consent has been signed and washout from previous medications is complete (when necessary), the following assessments will be performed as part of the subject eligibility assessment:

- MINI (Mini International Neuropsychiatric Interview)
- ATHQ (Antidepressant Treatment History Questionnaire)
- Mini Mental Status Exam (MMSE-2)
- Medical and psychiatric history
- Concomitant medication history
- Adverse Events
- Demographics
- NeoSync EEG

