The following Nutritional supplements are excluded throughout the study and should be washed out at least 1 week prior to baseline (Day 0):

- CQ-10

- Ginkgo Biloba
- Ginseng containing supplements
- Sam-E
- St John's Wort
- High doses of Omega-3 fatty acids and fish oil supplements (note: this is acceptable if subject is taking $\leq 1000\text{mg}$ QD or reported taking the supplements for at least one month prior to starting the study).
- HAM-D17 not available at Week 6.

The final major protocol violations will be reviewed and defined prior to unblinding the treatment randomization.

STATISTICAL ANALYSES

General Overview of Methods

This is a randomized, double-blinded, sham-controlled, parallel group study to evaluate the effectiveness of sTMS in subjects with Major Depressive Disorder (MDD). The objective of this study is to establish the efficacy of sTMS in comparison to sham treatment in subjects with major depressive disorder.

The primary endpoint is clinical response, defined by 50% or greater reduction on the HAM-D17 total symptom scores following 6 weeks of double-blind treatment (Week6).

The data analysis on the double-blind portion will be performed when all randomized subjects have completed the double-blind Week 6 visit or have withdrawn from the study prior to completion of the double-blind phase. The data analysis on the open-label portion will be performed when all open-label subjects have completed the Week 12 visit or have withdrawn from the study prior to the open-label Week 12 visit.

The standard descriptive statistics such as mean, standard deviation, median, quartiles, minimum, and maximum will be used to summarize the continuous variables. For discrete variables, the frequency and percentage of patients in each category will be calculated.

Sites with fewer than 10 subjects in the PP group will be pooled with other centers by geographic region prior to carrying out analyses described below. All statistical tests will be two-sided with a significant level of 0.05. All confidence intervals will be two-sided with a confidence level of 95%. Statistical analyses will be conducted with SAS Version 9.4 or larger.

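### The Week 6 change ANCOVAs leave out centre, the treatment-by-centre check as listed leaves out baseline, and neither matches the protocol's MMRM

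*SAP*

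**What the plan says.** **Main model.** SAP section H (Secondary Analyses for Label Considerations) compares mean change in HAM-D17 and MADRS at Week 6 by "analysis of covariance adjusting for the baseline value of the given endpoint". The imputed-data ITT analysis repeats this: "analysis of covariance comparing treatments adjusting for the baseline value of the endpoint". Neither names centre.

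**Pooling check.** The same section tests treatment-by-centre interaction for these two endpoints by what it also calls analysis of covariance, with the "independent variables of treatment group, investigative center, and the treatment-by-investigative interaction". No baseline score is listed. The test level is 0.15. A non-significant interaction, or a significant one judged only quantitative, supports pooling.

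**Randomisation.** Protocol section 3: "Randomization will be stratified by site in blocks of 10". SAP, Randomization: "at a 1:1 ratio stratified by study center".

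**Centres.** Protocol synopsis: "Multicenter, up to 16 clinical sites". SAP, General Overview of Methods: "Sites with fewer than 10 subjects in the PP group will be pooled with other centers by geographic region". The pooling is done before the blind is broken.

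**Protocol model.** Section 11.5 (Additional Endpoint Analyses) specifies for the same two endpoints an MMRM with treatment, centre, visit and treatment by visit, plus the baseline score as covariate. The SAP does not explain the change of model.

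**The concern.** A check that is meant to support pooling centres should be the main model with one addition, treatment-by-centre. Here the check adds centre and, as listed, drops baseline. The two models are not nested, and the check examines a different model from the one it is meant to support.

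Separately, the main model leaves out the factor that randomisation balances on. If centres differ in mean change, that variation stays in the residual and the treatment standard error is larger than it needs to be.

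What is at stake is modest but real. These are label endpoints tested in a fixed order. HAM-D17 change comes first after the primary, and testing stops at the first p-value above 0.05. Precision lost there can also close off MADRS change and MADRS response.

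**Working it through.** **The plan's own figures.** The only sizing figure is 81% power with 46 PP subjects per arm for the primary Fisher's exact test (34% vs 8%). A continuity-corrected formula gives 81.4% and direct enumeration of the exact test gives 83.6%. This point does not depend on that figure. No power or precision is stated for either ANCOVA.

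**Terms side by side**

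| Model | Treatment | Baseline | Centre | Treatment x centre |
|---|---|---|---|---|
| Protocol 11.5 MMRM (also visit, treatment x visit) | yes | yes | yes | no |
| SAP H main ANCOVA, available and imputed data | yes | yes | no | no |
| SAP H pooling check | yes | not listed | yes | yes |

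**Inputs from the documents**
- 92 PP subjects, 46 per arm (SAP, Sample Size).
- SD of HAM-D17 change in the earlier trial's non-naive completers, 7.33 and 4.74 (protocol 1.1): sqrt((7.33² + 4.74²)/2) = 6.17.
- Differences from the earlier trial: 7.39 - 4.59 = 2.80 (non-naive completers) and 8.58 - 4.25 = 4.33 (non-naive PP).
- Pooled centres of at least 10 PP subjects: 92/10 = 9.2, so at most about nine.

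**Assumptions, not in the documents:** the share of residual variance due to centre (rho), the baseline-to-change correlation (r), and the SD of the treatment effect across centres (tau). The SD of 6.17 is a raw SD standing in for the residual SD. This affects the power figures but not the width ratios.

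**(a) Adding pooled centre to the main model.** Standard error without centre = 6.17 x sqrt(2/46) = 1.287. Residual df fall from 92 - 3 = 89 to 89 - 8 = 81. Ratio of CI widths = sqrt(1 - rho) x t(0.975, 81)/t(0.975, 89) = sqrt(1 - rho) x 1.9897/1.9870. Power is from the noncentral t.

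| rho | CI width ratio | Power for 2.80 (57.6% without centre) | Power for 4.33 (91.4% without centre) |
|---|---|---|---|
| 0 | 1.001 | 57.5% | 91.4% |
| 0.05 | 0.976 | 59.7% | 92.7% |
| 0.10 | 0.950 | 62.0% | 93.9% |
| 0.20 | 0.896 | 67.1% | 96.0% |

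**Validity.** A simulation used nine centres of 10, exact 1:1 balance within centre, r = 0.3 and 4,000 runs per setting. With no treatment effect, the ANCOVA without centre rejected in 4.8%, 4.1%, 4.4% and 3.0% of runs at centre shares of total variance of 0, 5, 10 and 20%. With centre, rejection lay between 4.6% and 5.5%. The Monte Carlo standard error is sqrt(0.05 x 0.95/4000) = 0.34 points. Leaving out centre therefore does not inflate type I error, and the test becomes conservative as centres differ more.

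**(b) Leaving baseline out of the check.** The residual SD is multiplied by 1/sqrt(1 - r²): 1.021, 1.048, 1.091 and 1.155 for r = 0.2, 0.3, 0.4 and 0.5, and 1.000 for r = 0. The noncentrality of the interaction F test with equal centres is N x tau²/(4 x SD² x (1 - r²)). With tau = 3 points:
- no baseline: 92 x 9/(4 x 6.17²) = 5.44, on 8 and 74 df; power at the 0.15 level is 51.0%;
- with baseline, r = 0.3: 5.44/0.91 = 5.98, on 8 and 73 df; power 54.2%;
- with baseline, r = 0.5: 5.44/0.75 = 7.25, on 8 and 73 df; power 61.5%.

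**The case against.** A reader might infer more than the documents support in four ways.

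- *Both models lose precision on the treatment effect.* Only the main model can. The check yields no reported treatment estimate or interval, so leaving out baseline lowers only the power of a pooling check. That check already uses a liberal 0.15 level, and the SAP names no alternative analysis if it is significant.
- *The SAP chose to drop baseline.* It may be loose wording. The model is called analysis of covariance, and the other ANCOVAs for treatment comparisons in sections H and I are stated as baseline-adjusted. A programmer would still implement the listed terms, so the text needs settling either way.
- *The secondary results would be invalid, or the primary weakened.* Neither follows. The main ANCOVA is valid or conservative, and the primary Fisher's exact test uses neither model.
- *The gain is assured.* It is not. If centres do not differ, adding centre widens the interval by about 0.1%. The entry threshold of HAM-D17 at least 17 may also weaken the baseline-to-change correlation.

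Two further objections stand in part. Pooled centre is not the randomisation stratum itself: 92/16 = 5.75 PP subjects per site if all 16 sites open, so many sites could be merged, and regions may explain less variance than sites. Balance within site will also be only approximate, since 120/16 = 7.5 enrolled per site is less than one block of 10 and about 23% are expected to leave the PP set. The simulated exact balance is therefore the favourable case. Both points make the size less certain. Neither is a reason to leave the term out, and a centre term also protects against within-centre imbalance.

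**Conclusion.** The point holds as a low-cost improvement to two gated secondary endpoints. It is not an error of validity. On the text, the main ANCOVA omits centre despite stratified randomisation, the check as listed omits baseline and so is not the main model plus an interaction, and the protocol has both terms in one model.

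The size rests on assumed values. For a centre share of 0% to 10% of residual variance, the confidence interval would change by between +0.1% and -5%. Power for a 2.80-point difference would move from 57.6% to between 57.5% and 62.0%. In the nine-centre example with tau = 3 points, adding baseline raises the power of the pooling check by about 3 points (r = 0.3) to about 11 points (r = 0.5), and by nothing if r = 0.

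The firmest finding needs no assumption: the protocol and SAP give different models for the same endpoints, and the SAP does not say why.

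**What to change.** Before unblinding, amend SAP section H as follows.

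1. Main model for Week 6 change in HAM-D17 and MADRS: treatment, baseline score of the endpoint, and pooled centre. Use the same terms for available and imputed data.
2. Pooling check: that same model plus treatment-by-centre, with baseline named explicitly.
3. Reconcile with protocol section 11.5. State whether the MMRM or the Week 6 ANCOVA is the label analysis, why, and what role the other has. Changing the ANCOVA terms alone would leave the two documents in conflict.

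The cost is a few sentences and, with nine pooled centres, 8 residual degrees of freedom in the main model and 1 in the check. No new data are needed: baseline is already collected, and centre pooling is already to be fixed before the blind is broken.
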